9.5.2.2 Testing Accuracy

Pearson's correlation coefficient will be computed to quantify the strength of the direction of the linear relationship between the venipuncture collection and the Tasso+™ collection at Day 1 for each cohort for SARS-CoV-2 serology and each chemistry analyte.

Any participant who is positive for IgG Nucleocapsid assay for either matrix (SST or EDTA), will be considered SARS-CoV-2 positive.

Contingency correlation coefficient will be computed to estimate the extent of the relationship between the venipuncture collection and the Tasso+™ collection at Day 1 for each cohort for SARS-CoV-2 serology.

This analysis will be presented for both the FAS and PPS.

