Establishing correlation coefficients of laboratory results collected by a study participant and compared to standard venipuncture will be an important milestone to rely solely on the patient/study participant to self-collect blood using either device/kit collected and to ship the samples to a designated laboratory. Indeed, in a recent study, even though Tasso/SST serum protein measurements were highly reproducible, self-collection at home with delayed sample processing was associated with significant concentration differences for several analytes compared to supervised, in-clinic collection with rapid processing ([Brandsma et al., 2022](#)). These results are to be compared to higher concordance results obtained among other studies focusing on serology: overall accuracy of 98.9% in the study conducted by [Hendelman et al., \(2021\)](#) and Cohen's kappa coefficient of 0.88 in the study conducted by [Wixted et al., \(2022\)](#).

The sample integrity of Tasso+™/SST (ie, adequate volume and absence of moderate or gross hemolysis) and Tasso+™/EDTA (ie, adequate volume, absence of moderate or gross hemolysis, and absence of clotting) capillary collection tubes will be evaluated on Day 1 for each cohort and on each of Days 29 and 57 for Cohorts A and B combined ([Table 4](#)).

Table 4 Sample Testing Table

Method of blood collection	Laboratory Results		Sample Integrity		
	SARS-CoV-2	Chemistry*	Sample Volume	Hemolytic Index	Clotting
Tasso+™ device	EDTA	✓	✓	✓	✓
	SST	✓	✓	✓	✓
Venipuncture	EDTA	✓			
	SST	✓	✓		

EDTA=ethylenediaminetetraacetic acid; SST=serum separator tube

Footnotes: Chemistry analytes include sodium, potassium, chloride, blood urea nitrogen, creatinine, glucose, phosphate, uric acid, and C-reactive protein.

There will be no complete blood count laboratory analysis using Tasso+™/EDTA capillary collection tube due to potential for red cell lysis and clotting, and insufficient blood volume collection that may preclude accurate results.

The impact of the timing of centrifugation after blood collection with Tasso+™ on blood sample integrity and accuracy will be evaluated on Day 1, as Tasso+™ blood samples of Cohort A participants will be centrifuged after shipping to the Central Laboratory, while Tasso+™ blood samples of Cohort B participants will be centrifuged and aliquoted by the Site prior to being shipped to the Central Laboratory alongside with venipuncture blood samples that will be centrifuged prior to shipping as per standard procedures.

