6.3.2 Testing Accuracy

Testing accuracy of the Tasso+™ device, as part of device performance, will be evaluated as (i) the correlation of SARS-CoV-2 serology between venipuncture and either Tasso+™/SST or Tasso+™/EDTA samples collected on Day 1; and (ii) the correlation of each chemistry analyte between venipuncture and Tasso+™/SST samples collected on Day 1. This endpoint will only be assessed on Day 1 for each cohort separately.

Seroconversion will be evaluated using IgG Nucleocapsid assay. A total serum (SST) or plasma (EDTA) volume of 175 µL will be necessary to cover potential retesting, if needed. Any participant who is positive for IgG Nucleocapsid assay for either matrix (SST or EDTA), will be considered SARS-CoV-2 positive.

The following chemistry analytes will be assessed for correlation between the two collection approaches (venipuncture and Tasso+™/SST) on Day 1: sodium, potassium, chloride, blood urea nitrogen, creatinine, glucose, phosphate, uric acid, and C-reactive protein.

Noteworthy, in case of long duration between sample collection and testing, there may be risks associated with inaccurate sodium, potassium, and glucose values.

If a sodium, potassium, or glucose level is determined by the PI to be possibly clinically significant, a venipuncture repeat of the test should be performed at the Investigator site for safety reasons. Testing will be performed by the Investigator site and will not be sent to the Central laboratory.

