9.4.2 Secondary Endpoints

9.4.2.1 Safety

Counts and percentages will be presented for participants in the FAS who experience:

- Solicited local AEs (including pain, tenderness, redness, swelling, or bruising)

- Unsolicited AEs
- A related Grade 3 AE
- A related Grade 4 AE
- A related AE leading to discontinuation
- A related SAE

9.4.2.2 *Tolerability*

The counts and percentages of participants in the FAS who complete the Day 57 Visit will be summarized.

9.4.2.3 *Usability*

Descriptive statistics will be presented for participants in the FAS for each aspect of the usability questionnaire on Days 1, 29, 57, and 85.

9.4.2.4 *SARS-CoV-2 Infection Surveillance*

Counts and percentages will be presented for participants in the FAS for:

- Participants with a positive nasopharyngeal swab for SARS-CoV-2 PCR on Day 1
- Participants seroconverting to SARS-CoV-2 between Days 1 and 57

9.4.3 *Exploratory Endpoint*

Descriptive statistics will be presented for participants who requested proctor support on Day 57 Visit and for participants who completed the Day 57 Visit without using the proctor support, for the following primary and secondary endpoints:

- Sample integrity
- Reliability
- Safety
- Usability

9.4.4 *Analysis of Safety*

The SAS will be used for the analysis of safety data.

AEs will be coded with MedDRA. AEs are defined as events with an onset date on or after the date of first administration of the medical device and before the date of last administration of the medical device (Visit 3, Day 57 ± 3) +28 days, which corresponds to the Visit 4 (Day 85 ± 3). TEAEs will be presented by system organ class and preferred term in frequency tables. Participants with multiple AEs will be counted only once within each preferred term and system organ class.

Laboratory data (sodium, potassium, chloride, blood urea nitrogen, creatinine, glucose, phosphate, uric acid, and C-reactive protein) will be converted to Système International units for reporting and processing purposes. Absolute values will be presented descriptively. Laboratory data outside study-specific reference ranges will be listed.

9.4.5 *Demographic and Baseline Characteristics*

Demographic characteristics (including age, sex, ethnicity, and race) and baseline characteristics (including height, weight, BMI, supine systolic and diastolic blood pressure, pulse, body temperature, and respiratory rate) will be presented descriptively.

Prior and concomitant medications will be listed.

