9.5 Efficacy Analyses

9.5.1 Hypothesis Testing Strategy and Multiplicity

Hypothesis testing strategy and multiplicity are not applicable for this study.

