9.5.4.3 Testing Accuracy

A stratified testing accuracy analysis will be conducted using the following two strata:

- Samples received by the central laboratory \leq 1 day after collection (ie, received by the central laboratory either on the same day as collection or the day following collection)
- Samples received by the central laboratory $>$ 1 day after collection

Contingency correlation coefficient will be computed to estimate the extent of the relationship between the venipuncture collection and the Tasso+™ collection at Day 1 by cohort for each biochemistry parameter.

This stratified analysis will be conducted in the PPS.

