9.6.4 Laboratory Data

Laboratory data (sodium, potassium, chloride, blood urea nitrogen, creatinine, glucose, phosphate, uric acid, and C-reactive protein) will be converted to the International System of Units (SI) for reporting and processing purposes. Laboratory data outside study specific reference ranges will be highlighted within the listing.

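### Pearson's r is the only primary statistic for chemistry accuracy; it cannot show a constant or proportional Tasso+/venous difference, and no paired bias or agreement analysis is planned

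*SAP*

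**What the plan says.** Protocol 3.1 defines chemistry testing accuracy as the Day 1 correlation of each analyte between venipuncture and Tasso+/SST samples, for each cohort. Protocol 9.4.1.2 and SAP 9.5.2.2 name the statistic: "Pearson's correlation coefficient will be computed to quantify the strength of the direction of the linear relationship". It is reported for the FAS and the PPS. SAP 9.5.2.2 adds a contingency coefficient for serology only.

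The other planned outputs that touch chemistry are:

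- SAP 9.5.4.3, exploratory, in the PPS: a contingency coefficient "at Day 1 by cohort for each biochemistry parameter", stratified by whether the sample reached the laboratory within one day. No categories are defined for the continuous analytes.
- Protocol 9.4.4, under safety: "Absolute values will be presented descriptively".
- SAP 9.6.4: "Laboratory data outside study specific reference ranges will be highlighted within the listing".
- SAP 9.5.4.4: the share of subjects with a complete analyte profile.
- Protocol 9.1 and SAP 9.0: general rules for summarising continuous variables.

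Protocol 1.2 says the impact of centrifugation timing "on blood sample integrity and accuracy will be evaluated on Day 1", using the contrast between Cohort A (centrifuged after shipping) and Cohort B (centrifuged at the site). SAP 9.5.1 states "Hypothesis testing strategy and multiplicity are not applicable for this study".

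**The concern.** To judge whether a self-collected chemistry value can stand in for a venous one, a reader needs the size and direction of any difference and how much it varies. Pearson's r gives neither size nor direction. An analyte that reads uniformly high or low can show a high r and be taken as accurate. An unbiased analyte with a narrow healthy range can show a modest r and be taken as inaccurate.

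The protocol itself treats level errors as possible. Section 1.2 cites a serum-protein study in which measurements were highly reproducible, yet after home collection "delayed sample processing was associated with significant concentration differences for several analytes". Section 6.3.2 warns that "in case of long duration between sample collection and testing, there may be risks associated with inaccurate sodium, potassium, and glucose values".

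The centrifugation question is affected in the same way. If late centrifugation moves every Cohort A result by a similar amount, the two cohort correlations will look alike and the effect will not be seen.

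**Working it through.** The documents give no power, margin, SD or allowable error, so there is no design figure to reproduce beyond the allocation: 200 × 2/3 = 133.3 and 200 × 1/3 = 66.7, which match the stated 133 and 67. All analyte SDs and shifts below are assumptions for illustration.

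**Model.** Venous value has SD s. Tasso+ = k × venous + shift + noise, with noise SD e and between-sample shift SD v.

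- r = k·s / √(k²s² + e² + v²). The mean shift does not appear.
- Lin's concordance = 2·cov / (var₁ + var₂ + bias²), with cov = k·s².

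**Potassium-like, uniform shift** (s = 0.35, e = 0.15 mmol/L, k = 1, v = 0). r = 0.35/√(0.1225 + 0.0225) = 0.919. Concordance = 0.245/(0.2675 + shift²).

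| Shift (mmol/L) | r | Concordance |
|---|---|---|
| 0 | 0.919 | 0.916 |
| +0.2 | 0.919 | 0.797 |
| +0.5 | 0.919 | 0.473 |
| +1.0 | 0.919 | 0.193 |

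**Shift that varies between samples.** With a mean shift of +0.5:

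- v = 0.15: r = 0.35/√0.1675 = 0.855
- v = 0.25: r = 0.35/√0.2075 = 0.768

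Here r does fall, but it still does not give the bias.

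**Glucose-like, proportional loss** (mean 92, s = 12, e = 3 mg/dL, noise added after the loss).

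| Loss | r | Concordance | Bias (mg/dL) |
|---|---|---|---|
| 0% | 0.970 | 0.970 | 0 |
| 5% | 0.967 | 0.900 | −4.6 |
| 10% | 0.964 | 0.732 | −9.2 |
| 20% | 0.954 | 0.395 | −18.4 |

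If the noise shrinks with the signal, r stays at 0.970 throughout.

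**Sodium-like, no bias** (s = 1.5 to 2.5, e = 1.0 to 2.0 mmol/L). The lowest r is 1.5/√(2.25 + 4) = 0.600 and the highest is 2.5/√(6.25 + 1) = 0.928. A modest r is possible with perfect mean agreement.

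**Cohort comparison.** Simulation with 20,000 replicates, 133 and 67 participants, potassium-like values, and the shift in Cohort A only. The table shows how often each 95% CI excludes zero. The SAP plans neither interval; the interval for the difference in r (Fisher z) stands in for comparing the two cohort correlations.

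| Shift in A (mmol/L) | Difference in r | A − B mean bias |
|---|---|---|
| +0.1, uniform | 4.9% | 99.4% |
| +0.2, uniform | 4.8% | 100% |
| +0.5, uniform | 4.8% | 100% |
| +0.5, v = 0.15 | 53.7% | 100% |
| +0.5, v = 0.25 | 96.4% | 100% |

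Under a uniform shift, the comparison of correlations performs at chance level.

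**Precision available.** The 95% CI half-width for the A − B difference in mean bias is t × 0.15 × √(1/n_A + 1/n_B). This is 0.044 mmol/L at 133/67. If only 70% give a usable pair (the lower adequate-sample rate quoted in Protocol 1.2), n is about 93/47 and the half-width is 0.053.

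**Does the exploratory coefficient fill the gap?** The contingency coefficient is √(χ²/(χ² + n)). For an illustrative 2×2 table of 133 pairs, perfect agreement (60/0/0/73) and total disagreement (0/60/73/0) both give χ² = 133, so both give √(133/266) = 0.707. It measures association without direction.

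**The case against.** The strongest reply is that the endpoint is defined as a correlation, the protocol and SAP agree on it, and the SAP estimates what was defined. The study is descriptive, with no threshold or formal sample size, so no planned decision can go wrong. That stands. It limits the concern to how r will be read, but it does not make r an answer to an objective worded as accuracy.

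Second, the general descriptive rules, together with the absolute values promised in Protocol 9.4.4, could produce Tasso+ and venous means. On complete pairs, the difference between those means equals the mean paired bias. But nothing says the summaries will be split by collection method or restricted to pairs, and SAP 9.5.2.2 and 9.6.4 do not carry them forward. This narrows the gap without closing it.

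Third, Table 5 in Protocol 6.3.1 invalidates potassium and phosphate results at moderate hemolysis and all results at gross hemolysis. That is a real safeguard against one source of bias. It does not address delay effects in samples that pass.

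Fourth, the evidence for level error is indirect. The cited study measured serum proteins after home collection, whereas the comparison here is of chemistry analytes collected in clinic. The uniform-shift case is also the one most favourable to the concern. SAP 9.5.4.3 stratifies by receipt time, so transit time is expected to vary, and r then responds in part. Both points are fair. The warning about sodium, potassium and glucose, however, concerns this study's own analytes, and a lower r still would not show the size or direction of a bias.

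**Conclusion.** The concern holds and should be fixed. Pearson's r is the sole primary statistic for chemistry accuracy, and neither document plans a paired bias or agreement analysis. As planned, the results could not show how far, or in which direction, Tasso+ values depart from venous ones, or whether late centrifugation moves them.

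That r is unaffected by a constant shift is exact and needs no assumption. The sizes shown depend on assumed SDs, noise and shifts, and would differ by analyte. Where bias varies between samples, r is partly sensitive to it.

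**What to change.** Keep Pearson's r as the defined primary endpoint. Add to SAP 9.5.2.2, labelled as supplementary, for each analyte and cohort:

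1. the number of evaluable Day 1 pairs after hemolysis invalidation;
2. the mean paired Tasso+ minus venous difference (absolute or percent) with 95% CI;
3. Bland-Altman 95% limits of agreement, on a log or percent scale for C-reactive protein.

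Also report, for each analyte, the Cohort A minus Cohort B difference in mean bias with 95% CI as the centrifugation-timing estimate. Lin's concordance, or a Deming or Passing-Bablok slope and intercept, is optional. State that no analyte will be described as accurate on r alone.

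SAP v2.0 is already final, Protocol 9.1 says analysis personnel are unblinded, and SAP 9.5.2.1 refers to Cohort B Day 1 integrity records as already collected. The addition should therefore carry its date and say whether results had been seen.

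The cost is a short SAP addition and a few tables from pairs already in the plan, with no extra participants or samples. The results may look less favourable. Unless the sponsor sets an allowable error per analyte, which the documents do not give, the bias estimates stay descriptive.

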3 STUDY ENDPOINTS

3.1 Primary Endpoints

The primary endpoints that will be evaluated to assess the Tasso+™ blood collection device performance are as follows:

Sample integrity

- Percentage of overall Tasso+™/SST samples collected that are with adequate volume and without moderate or gross hemolysis on Day 1 for each cohort and on each of Days 29 and 57 for Cohorts A and B combined
- Percentage of overall Tasso+™/EDTA samples collected that are with adequate volume, without moderate or gross hemolysis, and without clotting on Day 1 for each cohort and on each of Days 29 and 57 for Cohorts A and B combined

Testing accuracy

- Correlation of SARS-CoV-2 serology between venipuncture and Tasso+™/SST or Tasso+™/EDTA samples on Day 1 for each cohort
- Correlation of each chemistry analyte between venipuncture and Tasso+™/SST samples on Day 1 for each cohort

Reliability

- Percentage of Tasso+™ device failures from Day 1 to Day 57 (see details in [Section 6.3.3](#)), defined as:
 - failure in activation of the lancet;
 - lack of any blood collection within 5 minutes;
 - incorrect attachment of the capillary collection tube to the device;
 - damage to the device or the capillary collection tube upon handling;
 - lack of maintained seal between the device and the skin surface of the participant; or
 - incomplete trigger of the button (not fully pressing the button once the Tasso+™ device is sealed to the skin surface).

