Each Tasso+™ capillary blood collection will be followed by a 28-day follow-up period during which safety of the Tasso+™ device will be assessed using an eDiary (Symptom questionnaire). Solicited symptoms will be assessed for the first 7 days following each Tasso+™ administration, while unsolicited AEs will be captured for the full 28-day period after each administration.

Each self-collected Tasso+™ blood sample will be assessed for sample integrity by the Central Laboratory. Moreover, on Day 1, the self-collected capillary blood sample will be compared to a venous blood sample collected by an HCP, in order to assess device performance.

Each participant will receive nasopharyngeal swabbing on Day 1 for SARS-CoV-2 PCR testing to identify any baseline SARS-CoV-2 infections. The nasopharyngeal swab will be performed and resulted by the Site. Participants with positive results may remain on study but will be referred to their primary physician for COVID-19 management. During the study, if participants experience any COVID-19 symptoms or if they became COVID-19 positive, they are to be reported to the Investigator via provided Site's phone number. Management of COVID-19 positive participants is detailed in [Section 4.4](#). SARS-CoV-2 antibody testing (Days 1 and 57) will be conducted to serologically identify intervening COVID-19 cases, or if in the absence of intervening symptoms, SARS-CoV-2 infections.

The Study Schematic and Schedule of Assessments are available in [Figure 1](#) and [Table 1](#) respectively.

See [Section 7.4](#) for an overview of instruction for use (IFU) of Tasso+™ device. The detailed IFU will be provided in a separate document.

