9.4.1.2 Testing Accuracy

Pearson's correlation coefficient will be computed to quantify the strength of the direction of the linear relationship between the venipuncture collection and the Tasso+™ collection at Day 1 for each cohort for SARS-CoV-2 serology and each chemistry analyte. This analysis will be presented for both the FAS and PPS.

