6.2 Randomization

Each participant will have a unique subject screening number obtained from the interactive voice response system (IVRS). Once the participant is deemed eligible, the participant will be assigned a randomization number.

Randomization will be performed via a centralized IVRS. On Day 1, eligible participants will be assigned to either Cohort A or Cohort B in a 2:1 ratio. Thus, it is planned to randomize approximately 133 participants into Cohort A and approximately 67 participants into Cohort B.

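### The only primary accuracy statistic for C-reactive protein is Pearson's r, by default on the raw scale, so one or two high values could dominate the reported coefficient

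*SAP*

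**What the plan says.** Protocol 3.1 lists as a primary endpoint "Correlation of each chemistry analyte between venipuncture and Tasso+™/SST samples on Day 1 for each cohort". Protocol 6.3.2 names the analytes: "sodium, potassium, chloride, blood urea nitrogen, creatinine, glucose, phosphate, uric acid, and C-reactive protein".

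Protocol 9.4.1.2 gives the method: "Pearson's correlation coefficient will be computed to quantify the strength of the direction of the linear relationship" between the two collections. SAP 9.5.2.2 repeats it (the coefficient "will be computed to quantify the strength of the direction of the linear relationship") and applies it in both the FAS and the PPS. Neither section states a scale, a transformation, a rank correlation, a rule for influential values, a scatter plot or an analysis of paired differences for chemistry.

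Two other SAP passages come close but do not fill the gap. The contingency coefficient in 9.5.2.2 is for serology. The one in 9.5.4.3 covers chemistry, but it is exploratory, confined to the PPS, and not a measure of agreement for a continuous result. SAP 9.6.4 highlights out-of-range laboratory results in a listing.

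The SAP sets no hypothesis test (9.5.1), and neither document gives an acceptance limit for r. SAP 6.2 plans "approximately 133 participants into Cohort A and approximately 67 participants into Cohort B".

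**The concern.** Pearson's r weights each pair by its distance from the mean on both axes. It describes a cohort well when values are spread fairly evenly, and poorly when most are bunched and one or two lie far away.

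The eligibility rules make a bunched CRP distribution with a few high values plausible. Participants are healthy or in well-compensated health (Protocol 5.1). Exclusion criterion 7 (Protocol 5.2) nevertheless admits acute illness judged mild, and on the Day 1 PCR test Protocol 4.1 says: "Participants with positive results may remain on study".

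Protocol 1.2 treats these coefficients as an important step towards relying on self-collected blood alone. With no acceptance limit, readers will judge the device by the size of r. For CRP, that size could depend largely on whether one inflamed participant happened to fall in the cohort.

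**Working it through.** **Inputs from the documents.** About 200 participants randomized 2:1: 200 × 2/3 = 133.3 and 200 × 1/3 = 66.7, which reproduces the planned 133 and 67. There is no power or precision figure to reproduce. These are maximum numbers of pairs; lost or invalid samples would raise the weight of a single pair.

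**Inputs assumed.** CRP log-normal with median 1.5 and log-SD 0.8. Only the ratio of the high value to the median matters, so the unit is immaterial. Venous and capillary values are unrelated except in one participant, who has the same high value in both tubes. Zero association elsewhere is deliberately the extreme case: it shows what r cannot rule out.

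**Step 1, by formula.** Let *m* pairs lie *k* SDs from the mean of the rest on both axes, with r = 0 among the remaining *n* − *m*. Then

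r = E / ((n − m − 1) + E), where E = m(n − m)k²/n.

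Under the assumed distribution the mean is 1.5 × exp(0.8²/2) = 2.07 and the SD is 2.07 × √(exp(0.64) − 1) = 1.96. One value of 40 gives k = (40 − 2.07)/1.96 = 19.35 and k² = 374.5.

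- n = 67: E = (66/67) × 374.5 = 368.9; r = 368.9/(65 + 368.9) = 0.85.
- n = 133: E = (132/133) × 374.5 = 371.7; r = 371.7/(131 + 371.7) = 0.74.

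In general, for one pair to bring r to 0.90 it must lie 24.4 SDs away at n = 67 or 34.5 SDs at n = 133. With two such pairs the distances are 17.2 and 24.4 SDs.

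**Step 2, by simulation**, same assumptions, median raw Pearson r:

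| Shared high value | n = 67 | n = 133 |
|---|---|---|
| 5 | 0.03 | 0.02 |
| 10 | 0.23 | 0.12 |
| 20 | 0.60 | 0.41 |
| 40 | 0.87 | 0.75 |
| 80 | 0.96 | 0.93 |

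The row for 40 agrees closely with the formula. Spearman's median stays at or below 0.05 throughout. For values of 20 to 80, log-scale Pearson is 0.14–0.27 (n = 67) and 0.07–0.16 (n = 133).

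**Step 3, a less extreme case.** With a true log-scale correlation of 0.5 in the rest of the cohort and one shared value of 40 (n = 67), raw r is about 0.93, log-scale r 0.61 and Spearman 0.51.

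**Step 4, the device works.** True values with log-SD 1.1, n = 67, 2.5th to 97.5th percentiles:

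| Error | Raw Pearson | Spearman |
|---|---|---|
| 30% in both tubes | 0.76–0.98 | 0.87–0.95 |
| 30% in one tube | 0.87–0.99 | 0.93–0.98 |
| 10% in both tubes | 0.97–1.00 | 0.98–0.99 |

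Raw r is the less stable measure when error is large. At 10% error there is nothing to choose between them.

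**Step 5, the opposite harm.** Take a cohort with median 1, log-SD 1.0, values below 10 and 10% error, where r = 0.99. One discordant pair (50 against 1) cuts raw r to 0.21 (n = 67) or 0.31 (n = 133). Log-scale r stays at 0.89 or 0.94.

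**Step 6, a remedy that does not help.** A concordance correlation on the raw scale follows raw Pearson almost exactly. With median 1, log-SD 1.0, n = 67 and one pair near 50, both are 0.94 although the rest of the cohort is unrelated.

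**The case against.** **The plan is internally consistent.** The protocol endpoint is a correlation, the protocol specifies Pearson, and the SAP implements it faithfully. The SAP does not forbid a log transformation; raw scale is only the default reading of its silence. This stands, and it is why raw Pearson should be kept.

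**Nothing is decided by r.** A reader might infer that one outlier could make the device pass or fail on accuracy. The documents do not support that: the analysis is descriptive, no threshold is set, and CRP is one of nine analytes reported separately. Nothing here extends to the other eight.

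**The skew is assumed.** A reader might infer that the CRP coefficient will be uninformative. The documents give neither a CRP distribution nor a count of mildly ill or PCR-positive participants. Exclusions 1, 3, 6 and 7 in Protocol 5.2 remove several sources of raised CRP. A value of 5 or 10 moves r little, and at 20 r would still not read as good. An r near 0.9 with no association elsewhere needs a value many times the median. So the effect could occur; it cannot be said to be likely.

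**An extreme value would be visible.** Protocol 9.4.4 presents absolute laboratory values descriptively, and SAP 9.6.4 highlights out-of-range results in the listing. That would show that a high value exists, but not how far r depends on it.

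**Rank and log-scale coefficients do not measure agreement either.** This is right. Like raw Pearson, they miss a constant proportional bias, so they need a difference analysis beside them.

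**Conclusion.** The point holds as a modest, low-cost improvement. Raw-scale Pearson alone could give a CRP coefficient dominated by one or two participants, in either direction, and no planned output would show how much of r rests on them.

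The size depends on the assumed distribution. One shared value of 20 to 80, against a median of 1.5, lifts r from about zero to 0.60–0.96 in a cohort of 67 and to 0.41–0.93 in a cohort of 133. Values of 10 or less have a small effect. If measurement error is about 10% and there is no discordant extreme pair, the planned coefficient serves as well as the alternatives. What is affected is the interpretation of one descriptive primary coefficient in each cohort, not a study conclusion.

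**What to change.** In SAP 9.5.2.2, keep the raw-scale Pearson coefficient for continuity with the protocol. For CRP, add by cohort:

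- Pearson's coefficient on log-transformed values and Spearman's coefficient;
- a scatter plot of Tasso+ against venous results;
- the mean paired log-difference, back-transformed to a geometric mean ratio, with limits of agreement.

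Set results below the reporting limit to that limit and state how many there were, since these create ties. Describe all the coefficients as measures of association, and use the ratio and its limits to speak about agreement.

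This uses data already planned and leaves the sample size unchanged. It costs a few output columns, one figure per cohort and a short explanation of the log scale. If CRP results have been seen before the text is changed, label the additions as supplementary.
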